**Novo Nordisk**

The endpoints will be summarised by treatment arm for all infants and further sub-divided in the following groups:

- Mother randomised as pregnant
- Mother randomised as pregnant and exposed to trial drug at some point during the pregnancy period
- Mother randomised as pregnant and not exposed to trial drug at any point during the pregnancy period
- Mother randomised as non-pregnant
- Mother randomised as non-pregnant and exposed to trial drug at some point during the pregnancy period
- Mother randomised as non-pregnant and not exposed to trial drug at any point during the pregnancy period

For the above mentioned endpoints summary statistics will be provided. Instead of summarising only as (yes/no) categories some endpoints will be categorised into (yes/no/Unaddressed) categories where 'Unaddressed' refer to cases where the parents did not consent to share information after delivery or did not complete the pregnancy outcome form and to withdrawn subjects who did not give any further information.

#### **Adverse events in the infants from delivery to final follow-up**

This endpoint will be summarised for infants related to safety analysis set for pregnant women.

It is unknown whether adverse events on the day of delivery occurred before or after the actual delivery, as exact times were not collected. Adverse events and deliveries on either side of midnight could also be coherent. Therefore, adverse events from 1 calendar day before delivery to final follow-up are included.

Adverse events will be coded using the most recent version of the MedDRA database.

Adverse events will be summarised descriptively for all infants and additionally sub-divided in the following groups:

- Mother randomised as pregnant
- Mother randomised as pregnant and exposed to trial drug at some point during the pregnancy period

Statistical Analysis Plan  
Trial ID: NN1250-4300  
UTN: U1111-1191-3018  
EudraCT No: 2017-000048-17

~~CONFIDENTIAL~~

Date: 27 January 2021  
Version: 2.0  
Status: Final  
Page: 29 of 34

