#### **Key assessments**

- HbA1c (central laboratory)
- Hypoglycaemic episodes
- Adverse events during the pregnancy period
- Adverse events in the foetus and infant

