#### Supportive pregnancy outcome endpoints

- Birth weight (kg)
- Pre-term delivery (delivery < 37 completed GWs) (yes/no)
- Early foetal death (delivery < 20 completed GWs) (yes/no)
- Perinatal mortality (death of foetus/infant between  $\geq 20$  completed GWs before delivery and < 7 completed days after delivery) (yes/no)
- Neonatal mortality (death of infant between  $\geq 7$  completed days after delivery and < 28 completed days after delivery) (yes/no)
- Presence of major abnormalities (classified according to EUROCAT) (yes/no)
- Live born infants (yes/no)
- Number of adverse events in the infant from delivery to final follow-up
- Neonatal hypoglycaemic episodes defined as plasma glucose  $\leq 1.7$  mmol/L (31 mg/dL) during the first 24 hours after birth or  $\leq 2.5$  mmol/L (45 mg/dL) between 24 hours and 48 hours after birth (yes/no)

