### 12.5 Adverse events related to pregnancies

The investigator must report information about the pregnancy, pregnancy outcome, and health of the newborn infant(s), as well as AEs in connection with the pregnancy and AEs in the foetus and newborn infant(s) until 2 months of age in the eCRF.

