### 12.5.2 Reporting adverse events on foetus and/or infant(s)

The investigator has to report relevant AEs in the foetus and newborn infant(s). The SAEs that must be reported include abnormal outcome, such as foetal death (including spontaneous or induced abortion), and congenital anomaly(-ies) (including those observed at gross examination or during autopsy of the foetus), as well as other pregnancy complications fulfilling the criteria of an SAE.

Adverse events pertaining to the foetus/infant must be reported with the foetus/infant as the subject of the AE. The forms and timelines for reporting AEs are defined in Sections [12.2](#) and [12.7.3](#).

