**Novo Nordisk**

### 12.5.3 Congenital anomaly

Details about the congenital anomaly(-ies) will be collected in the specific eCRF for pregnancy outcome after delivery. All congenital anomalies must be reported as an SAE, Section [12.5.2](#).

As events of congenital anomalies are crucial for the ongoing safety monitoring, all congenital anomalies will be monitored closely by the Data Monitoring Committee (DMC, Section [12.7.2](#)) and will be adjudicated by an independent adjudication committee (EAC, Section [12.7.3](#)).

If a congenital anomaly is observed at ultrasound during pregnancy and reported as an SAE, but not confirmed after birth, the AE description should be updated with “No adverse effect” or “No adverse drug effect” in the eCRF.

The EMA Guideline on the exposure to medicinal products during pregnancy classifies anomalies as congenital anomalies, major abnormalities or minor anomalies. Specific definitions for each major abnormality are included in the European network of population-based registries for the epidemiologic surveillance of congenital anomalies (EUROCAT).

Rates of congenital anomalies and malformations have in some studies been shown to be 4-5% in pregnant subjects with T1DM. The most common anomalies affect the central nervous system, heart, skeleton, kidneys, gastrointestinal tract or lungs.

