**Novo Nordisk**

### Supportive pregnancy outcome endpoints

- Birth weight (g)
- Pre-term delivery (delivery < 37 completed GWs) (yes/no)
- Early foetal death (delivery < 20 completed GWs) (yes/no)
- Perinatal mortality (death of foetus/infant between  $\geq 20$  completed GWs before delivery and < 7 completed days after delivery) (yes/no)
- Neonatal mortality (death of infant between  $\geq 7$  completed days after delivery and < 28 completed days after delivery) (yes/no)
- Presence of major abnormalities (classified according to EUROCAT) (yes/no)
- Live born infants (yes/no)
- Number of adverse events in the infant from day of delivery to final follow-up
- Neonatal hypoglycaemic episodes defined as plasma glucose  $\leq 1.7$  mmol/L (31 mg/dL) during the first 24 hours after birth or  $\leq 2.5$  mmol/L (45 mg/dL) between 24 hours and 48 hours after birth (yes/no)

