**Table 4–2 Overview of defined analysis sets**

Defined Analysis Set	Description
Full analysis set for pregnant women (FASpregnant)	Includes all randomised women who are pregnant during the trial. Subjects in the FAS pregnant will contribute to the evaluation “as randomised”.
Per protocol analysis set for pregnant women (PPpregnant)	Includes subjects from FAS pregnant who: 
 
• Have not violated any inclusion criteria
 
• Have not fulfilled any exclusion criteria
 
• Are exposed to trial drug at least the first four weeks after randomisation or, in case of termination of pregnancy within the first four weeks after randomisation, until time of termination of pregnancy.
 
 Subjects in the PP pregnant analysis set will contribute to the analysis according to the treatment received prior to potential discontinuation of randomised treatment. This will be referred to as contributing to the evaluation “as treated”.
Safety analysis set for pregnant women (SASpregnant)	Includes all randomised women exposed to at least one dose of trial product and who are pregnant during the trial. Subjects in the SAS pregnant will contribute to the evaluation “as treated”.

The primary endpoint and secondary efficacy endpoints are analysed using full analysis set for all pregnant women.

Statistical Analysis Plan  
 Trial ID: NN1250-4300  
 UTN: U1111-1191-3018  
 EudraCT No: 2017-000048-17

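### Adverse events recorded on the foetus and dated more than one calendar day before delivery have no planned AE or SAE summary

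*SAP*

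**What the plan says.** **Collection.** The Protocol Summary lists "Adverse events in the foetus and infant" among its key assessments. Protocol 12.5 has the investigator report "AEs in the foetus and newborn infant(s) until 2 months of age in the eCRF". Section 12.5.2 fixes the subject of each record: "Adverse events pertaining to the foetus/infant must be reported with the foetus/infant as the subject of the AE". Section 12.5.3 allows for such records arising before birth, in an instruction that opens "If a congenital anomaly is observed at ultrasound during pregnancy and reported as an SAE" and goes on to the case where the finding is not confirmed afterwards.

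**Analysis.** The protocol endpoint (4.4) is "Number of adverse events in the infant from delivery to final follow-up". The SAP endpoint list (1.1.2.2) has "Number of adverse events in the infant from day of delivery to final follow-up". SAP 5.4.3 then gives the window to be used, and 6.2.2 repeats it as a change from the protocol: "Therefore, adverse events from 1 calendar day before delivery to final follow-up are included". The stated reason is that clock times were not collected, and that an event and a delivery on either side of midnight may belong together.

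The AE tables that do cover pregnancy are in the maternal safety sections (Protocol 17.4.2.2, SAP 5.4.2.1). The default population there is SAS_pregnant, defined in SAP Table 4–2: "Includes all randomised women exposed to at least one dose of trial product and who are pregnant during the trial".

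**The concern.** Data collection covers the foetus throughout pregnancy, but the offspring tables begin almost at birth and the tables that span pregnancy count women. An event filed under the foetus in mid-pregnancy falls between the two.

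Pregnancy outcome is a secondary objective, and Protocol 3.1 states that insulin degludec had not been tested in a clinical trial with pregnant subjects. The interval without an offspring AE summary is the period of in utero exposure. If the window is applied by onset date, whether a condition reaches the AE tables would also depend on when it was detected, and so partly on local scanning practice.

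**Working it through.** There is no planned figure to reproduce. The check is to ask, for each planned summary, whether it would receive an AE recorded on the foetus some weeks before delivery.

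| Planned summary | Counts | Period | Receives it? |
|---|---|---|---|
| Pregnancy-period TEAEs (Protocol 17.4.2.2, SAP 5.4.2.1) | women in SAS_pregnant | conception or randomisation to delivery | period fits, subject does not |
| In-trial, pre- and post-pregnancy AEs (Protocol 17.4.2.2) | same maternal section | the period named | no provision for the foetus as subject |
| All SAEs, treatment-emergent or not (same sections) | same maternal section | not restricted to treatment-emergent events | no provision for the foetus as subject |
| Infant AEs (Protocol 17.4.2.3) | infants | from delivery | no |
| Infant AEs (SAP 5.4.3) | infants of women in SAS_pregnant | from 1 calendar day before delivery | no |
| Major abnormalities, adjudicated (SAP 5.4.3) | infants or foetuses | no window stated | yes/no presence of a major abnormality only |
| Anomaly classification listing (Protocol 17.4.2.3) | anomalies | no window stated | class only |
| Early foetal death, perinatal mortality (SAP 5.4.3) | infants or foetuses | by definition | deaths only |

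The wording supports reading the AE summary as an infant summary. SAP 5.4.3 says that its outcome endpoints cover infants or foetuses, but for AEs it speaks of infants alone, and the Protocol glossary starts the infant at delivery.

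Taking the kinds of event in turn:

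- **Foetal AE other than an anomaly**, over before birth. It is recorded on the foetus, precedes the window and has no outcome endpoint. No AE table receives it.
- **Foetal diagnosis leading to induced abortion.** Protocol 12.5.2 requires the cause to be reported as an SAE on mother or foetus. The glossary counts termination as delivery. A foetal diagnosis dated two or more days earlier lies before the window.
- **Foetal death with a diagnosis.** The death is an SAE on the mother. Protocol 12.5.2 asks for an additional SAE on the foetus for the diagnosis, and that second SAE has no table if it predates the window.
- **Anomaly seen at ultrasound.** The AE form is due within 24 hours of first knowledge of an SAE (12.2), and worsening of an unresolved event is follow-up to the same record (12.3), so a record dated in pregnancy is to be expected. The major-abnormality endpoint and the listing still show presence and class. The severity, causality and SOC/PT counts by arm depend on how SAP 5.4.3 dates the event, which it does not state.

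**Scale.** The documents allow only a rough figure, and only for anomalies. Inputs: 188 women in the full analysis set for pregnant women (SAP 6.3.1.1) and the 4–5% anomaly rate cited in Protocol 12.5.3.

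188 × 0.04 = 7.5 and 188 × 0.05 = 9.4 expected anomalies, both arms together.

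The share dated before the window is not given. If it were 25% to 75% (an assumption), the range would be 7.5 × 0.25 = 1.9 to 9.4 × 0.75 = 7.1. This does not measure lost events, because it covers only anomalies, which have other outputs. For the other three kinds the documents give no rate.

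**The case against.** The case on the other side is substantial.

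- **Dating.** SAP 5.4.3 does not mention onset; the onset rule in Protocol 17.4.2.2 is in the maternal section. A finding still present at birth could be taken as inside the window. Protocol 8.4.2 also requires an anomaly seen at gross examination at delivery to be reported as an SAE, and 12.5.3 collects anomaly details after delivery. This stands. A reader might infer that a condition found on ultrasound is plainly dropped while the same condition found at birth is counted. The documents leave that case ambiguous.
- **Other outputs.** Foetal deaths are filed on the mother and have outcome endpoints. Major abnormalities are adjudicated, anomaly classifications are listed, and Protocol 12.7.3 puts both committee and investigator assessments in the trial report. This stands, so it would be wrong to infer that foetal problems go unreported.
- **The maternal tables do not expressly exclude foetal SAEs.** True, but nothing provides for them there, and counts of women are a poor place for events whose subject is the foetus.
- **The SAP follows the protocol endpoint**, which starts at delivery, and gives a reason for its extra day. Also true. The gap begins in the protocol; the SAP widened the window without adding a summary for earlier foetal events.

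**Conclusion.** The gap is real but narrow. AEs recorded on the foetus and dated earlier than one calendar day before delivery have no planned AE or SAE summary. It concerns the four kinds of event traced above; for anomalies, only the AE tabulation is at issue.

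Its size cannot be derived from the documents. A reader might turn the anomaly arithmetic into a count of SAEs missing from one arm. That is not supported: the share detected before birth is assumed, the anomalies have other outputs, and no mechanism is shown by which detection timing would differ between randomised arms. The tables are descriptive, and the primary conclusion is untouched.

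The conclusion rests on two readings: that AE tables in the maternal sections count events in women, and that infant in SAP 5.4.3 does not include the foetus before the stated window. For anomalies persisting to birth it also depends on the unstated dating rule, which needs stating on either reading.

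**What to change.** In SAP 5.4.3, and correspondingly in Protocol 17.4.2.3:

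1. Add to the existing offspring AE and SAE tables a separate block for AEs with the foetus as subject, with onset from first day of pregnancy or randomisation (whichever is later) to 2 calendar days before delivery. Use as denominator all foetuses of women in SAS_pregnant, including early losses and terminations. Show the same N, %, E, severity, relationship and SOC/PT breakdowns.
2. Keep the infant block from 1 calendar day before delivery, with infants as denominator. The two blocks then neither overlap nor share a denominator.
3. State the dating rule: either AEs are assigned by onset date, or events ongoing at birth are also counted as infant events.
4. Align the endpoint wording in SAP 1.1.2.2, which starts at the day of delivery, with the window in 5.4.3.

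Foetal observation starts at conception for women randomised non-pregnant and at GW 8–13 for those randomised pregnant; the subgroups already planned by pregnancy status at randomisation would show this.

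The protocol already requires these data in the eCRF. The cost is the rewording, one extra block per table and a slightly longer safety output.

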**Novo Nordisk**

- Mother randomised as pregnant and not exposed to trial drug at some point during the pregnancy period
- Mother randomised as non-pregnant
- Mother randomised as non-pregnant and exposed to trial drug at some point during the pregnancy period
- Mother randomised as non-pregnant and not exposed to trial drug at any point during the pregnancy period

The summaries will display the number of infants with at least one event (N), the percentage of infants with at least one event (%) and the number of events (E). Summaries will be presented as an overview including all AEs, serious AEs, AEs by severity and AEs by relation to treatment.

Furthermore, summary tables based on system organ class and preferred terms are made for:

- All AEs
- SAEs
- AEs possibly or probably related to trial product
- Severe, moderate and mild AEs
- AEs with preferred term that are experienced by at least 5% of the infants in any treatment or by at least 5% of all infants

## **5.5 Safety endpoints analysis**

Not applicable

## **5.6 Exploratory endpoint and other assessments analysis**

The exploratory endpoint listed in Section [1.1.2.3](#) and other assessments listed in Section [1.1.2.4](#) will be presented as per summary statistics.

For other assessments the summary statistics will be presented for safety analysis set pregnant.

## **5.7 Interim analyses**

No interim analysis is planned for the efficacy data in this trial.

### **5.7.1 Data monitoring committee**

Refer to [protocol section 12.7.2](#).

Statistical Analysis Plan  
Trial ID: NN1250-4300  
UTN: U1111-1191-3018  
EudraCT No: 2017-000048-17

~~CONFIDENTIAL~~

Date: 27 January 2021  
Version: 2.0  
Status: Final  
Page: 30 of 34

Novo Nordisk

## 6 Supporting documentation

### 6.1 Appendix 1 List of abbreviations

AE	adverse event
ALT	alanine aminotransferase
AP	alkaline phosphatase
AST	aspartate aminotransferase
BG	blood glucose
BID	bis in die (twice daily)
CGM	continuous glucose monitoring (including flash glucose monitoring)
CI	confidence interval
EAC	event adjudication committee
eCRF	electronic case report form
EMA	European Medicines Agency
EudraCT	European Clinical Trials Database
EUROCAT	European Concerted Action on Congenital Anomalies and Twins
FAS	full analysis set
FPG	fasting plasma glucose
GW	gestational week
HbA1c	glycosylated haemoglobin
hCG	human chorionic gonadotropin
HELLP	haemolysis, elevated liver enzymes, low platelet count
IAsp	insulin aspart
ICH	International Conference on Harmonisation of Technical Requirements for Registration of Pharmaceuticals for Human Use
IDeg	insulin degludec
IDet	insulin detemir
IMP	investigational medicinal product
MedDRA	Medical Dictionary for Regulatory Activities
OD	once daily

Statistical Analysis Plan  
Trial ID: NN1250-4300  
UTN: U1111-1191-3018  
EudraCT No: 2017-000048-17

~~CONFIDENTIAL~~

Date: 27 January 2021  
Version: 2.0  
Status: Final  
Page: 31 of 34

**Novo Nordisk**

*PE*            *pre-eclampsia*  
*PG*            *plasma glucose*  
*PP*            *per protocol*  
*PPG*          *post-prandial glucose*  
*SAE*          *serious adverse event*  
*SAP*          *statistical analysis plan*  
*SD*           *standard deviation*  
*SmPC*        *summary of product characteristics*  
*T1DM*        *type 1 diabetes mellitus*  
*TTT*          *treat-to-target*  
*US*           *ultrasound*  
*UTN*         *Universal Trial Number*

Statistical Analysis Plan  
Trial ID: NN1250-4300  
UTN: U1111-1191-3018  
EudraCT No: 2017-000048-17

~~CONFIDENTIAL~~

Date: 27 January 2021  
Version: 2.0  
Status: Final  
Page: 32 of 34

**Novo Nordisk**

## 6.2 Appendix 2: Changes to protocol-planned analyses

In this SAP the following changes are being made to the statistical consideration in the protocol are as elaborated below for :

### 6.2.1 Maternal safety endpoints

#### Pre-eclampsia

For Pre-eclampsia summary, the number and percentage of subjects experiencing PE as well as the event rate per 100 years of observation will be displayed.

### 6.2.2 Pregnancy outcome endpoints

- Birth weight of infants will be summarised in ‘g’ (grams) instead of kg
- It is unknown whether adverse events on the day of delivery occurred before or after the actual delivery, as exact times were not collected. Adverse events and deliveries on either side of midnight could also be coherent. Therefore, adverse events from 1 calendar day before delivery to final follow-up are included.
- Instead of summarising only as (yes/no) categories some endpoints will be categorised into (yes/no/Unaddressed) categories where ‘Unaddressed’ refer to the cases where either the parents of the infant have not given consent to share information after delivery or the subjects who were withdrawn from trial and they did not give any further information or if the subjects did not fill the pregnancy outcome form.

## 6.3 Appendix 3: Definition and calculation of endpoints, assessments and derivations

### 6.3.1 Endpoint derivations and assessments

#### 6.3.1.1 Steps involved in defining last planned visit prior to delivery after GW 16 (LPVISPD L) :

The 188 subjects who were in full analysis set for pregnant women only qualify for the statistical analysis , hence LPVISPD L will be defined for only these subjects.

**Step 1:** Subjects delivering before GW16 is excluded from the analysis and LPVISPD L is not defined

**Step 2:** For subjects with visit 79 as the last site visit, LPVISPD L is set to 79.

**Step 3:** For subjects with visit 59, 63, 67, 71, or 75 as the last site visit prior to delivery the following is done:

Statistical Analysis Plan  
Trial ID: NN1250-4300  
UTN: U1111-1191-3018  
EudraCT No: 2017-000048-17

~~CONFIDENTIAL~~

Date: 27 January 2021  
Version: 2.0  
Status: Final  
Page: 33 of 34

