Weekly phone contact number (P). For details see Section 2.4			P55A P55B P55C	P56 P57 P58	P60 P61 P62	P64 P65 P66	P68 P69 P70	P72 P73 P74	P76 P77 P78	P80 – P85	P87 P88 P89		P91			P91A	
Timing of visits, GW (gestational weeks), d (days)	-21d	GW8-13 +6d	GW8-13 +6d	GW12	GW16	GW20	GW24	GW28	GW32	GW36	–	V86 +28d	EOT +7d	EOT +30d	–	EOT-A +7d	EOT-A +30d
Visit window (days)				±7	±7	±7	±7	±7	±7	±7		+3	+5	+5	+3	+5	+5
Estimated date of conception	X																
Pregnancy ultrasound scan		X	X														
EFFICACY																	
2-point profile			X	X	X	X	X	X	X	X	X	X f			X		
9-point profile		X	X		X		X		X	X							
HbA 1c	X	X	X	X	X	X	X	X	X	X		X			X		
Fasting plasma glucose		X	X		X		X		X	X							
SAFETY																	
Adverse events	X	X	X	X	X	X	X	X	X	X	X	X	X	X	X	X	X
Pre-eclampsia					X	X	X	X	X	X	X	X			X	X	X
Hypoglycaemic episodes		X	X	X	X	X	X	X	X	X	X	X	X	X	X	X	X
Technical complaints	X	X	X	X	X	X	X	X	X	X	X	X	X	X	X	X	X
Haematology and biochemistry	X		X				X				X	X			X		
Urinalysis	X	X	X	X	X	X	X	X	X	X							
Body Weight	X	X	X	X	X	X	X	X	X	X							
Eye examination	X		X					X				X			X		
Vital signs	X	X	X	X	X	X	X	X	X	X		X			X		
Physical examination	X		X									X			X		
ECG	X																

Protocol Protocol-version-4 | XXXXXXXXXX | XXXX  
 NN1250 -4300

Protocol  
 Trial ID: NN1250-4300

UTN: U1111-1191-3018  
 EndraCT no.: 2017-000048-17

Date: 17 December 2020  
 Version: 4.0

Status: Final  
 Page: 20 of 110  
 Novo Nordisk

	Screening	Randomisation	Additional visits		Pregnancy period							Delivery	End of treatment and follow-up			Premature discontinuation		
			V55 a	V55D b	V59	V63	V67	V71	V75	V79	V86 c		V90 EOT	FU1 d	V92 FU2	V90A EOT-A	FU1-A d	V92A FU2-A
Site visit (V)	V1	V2 a	V55 a	V55D b	V59	V63	V67	V71	V75	V79	V86 c	V90 EOT	FU1 d	V92 FU2	V90A EOT-A	FU1-A d	V92A FU2-A	
Weekly phone contact number (P). For details see Section 2.4			P55A P55B P55C	P56 P57 P58	P60 P61 P62	P64 P65 P66	P68 P69 P70	P72 P73 P74	P76 P77 P78	P80 – P85	P87 P88 P89		P91			P91A		
Timing of visits, GW (gestational weeks), d (days)	-21d	GW8-13 +6d	GW8-13 +6d	GW12	GW16	GW20	GW24	GW28	GW32	GW36	--	V86 +28d	EOT +7d	EOT +30d	--	EOT-A +7d	EOT-A +30d	
Visit window (days)				±7	±7	±7	±7	±7	±7	±7		+3	+5	+5	±3	+5	+5	
OTHER ASSESSMENTS / PREGNANCY AND DELIVERY																		

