BG-meter start date b	(X)	(X)	(X)	(X)	(X)	(X)	(X)	(X)	(X)	(X)	(X)	(X)	(X)	(X)	(X)	(X)	(X)	
Insulin degludec cord blood												X						
Pregnancy outcome												X						
Delivery information												X						
Infant health status												X	X	X	X			
TRIAL MATERIAL																		
IWRS session	X	X	X	X	X	X	X	X	X	X	X	X				X		
Dispensing visit		X	X	X	X	X	X	X	X	X	X							
First date on trial product		X																
New dose of trial insulin		X	X	X	X	X	X	X	X	X	X	X						
Dose of trial insulin		X	X	X	X	X	X	X	X	X	X	X				X		
Last dose of trial product												X			X			
Drug accountability		X	X	X	X	X	X	X	X	X	X	X				X		
REMINDERS																		
End of treatment												X			X			
End of trial														X				
Sign-off case-book														X				
Attend visit fasting		X	X		X		X		X	X								

	Screening		Randomisation		Additional visits		Pregnancy period						Delivery	End of treatment and follow-up			Premature discontinuation		
	V1	V2 a	V55 a	V55D b	V59	V63	V67	V71	V75	V79	V86 c	V90 EOT	FU1 d	V92 FU2	V90A EOT-A	FU1-A d	V92A FU2-A		
Site visit (V)																			
Weekly phone contact number (P). For details see Section 2.4			P55A P55B P55C	P56 P57 P58	P60 P61 P62	P64 P65 P66	P68 P69 P70	P72 P73 P74	P76 P77 P78	P80 – P85	P87 P88 P89		P91			P91A			
Timing of visits, GW (gestational weeks), d (days)	-21d	GW8-13 +6d	GW8-13 +6d	GW12	GW16	GW20	GW24	GW28	GW32	GW36	–	V86 +28d	EOT +7d	EOT +30d	–	EOT-A +7d	EOT-A +30d		
Visit window (days)				±7	±7	±7	±7	±7	±7	±7		±3	±5	±5	±3	±5	±5		
Hand out and instruct in BG-meter	X																		
Hand out and instruct in diary	X	X	X	X	X	X	X	X	X	X	X	X			X				
Collect diary		X	X	X	X	X	X	X	X	X		X		X	X		X		
Hand out directions for use g		X																	
Training in trial product, pen-handling		X	X				X												
Make appointment for eye examination							X			X									

a The V1 and V2 site visits are only applicable for subjects randomised pregnant. The V55 site visit is only applicable for subjects randomised non-pregnant and becoming pregnant in the conception period of the trial.

b The additional site visit V55D is only applicable for subjects randomised pregnant before GW 12 or for subjects that were randomised non-pregnant and become pregnant in the conception period of the trial and have an ultrasound scan completed before GW 12.

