### **8.5.2 Fasting visits**

Subject must attend specific visits in a fasting condition as outlined in the flowchart Sections [2.1](#) and [2.3](#) for collection of an FPG blood sample. Fasting is defined as having consumed only water and taken no insulin at least eight hours prior to the visit. Non-antidiabetic medication(s) are to be taken.

If a subject attends a fasting visit in a non-fasting condition, blood sampling should be re-scheduled preferably within the visit window. If blood sampling has already been done before realising the subject was not fasting, only the FPG sample needs to be re-drawn.

Protocol  
 Trial ID: NN1250-4300  
 UTN: U1111-1191-3018  
 EndraCT no.: 2017-000048-17

CONFIDENTIAL

Date: 17 December 2020  
 Version: 4.0  
 Status: Final  
 Page: 45 of 110

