**Table 8-1 Time points for the 9-point profile collected 2 days before selected visits**

Time point	Two days before visit	One day before visit
Before breakfast	✓ a	✓ a
90 minutes after the start of breakfast	✓	
Before lunch	✓	
90 minutes after the start of lunch	✓	
Before main evening meal	✓ a	
90 minutes after the start of main evening meal	✓	
Before bedtime	✓	
At 4 am	✓	

a Measurements included in the 2-point profile

Protocol  
Trial ID: NN1250-4300  
UTN: U1111-1191-3018  
EudraCT no.: 2017-000048-17

~~CONFIDENTIAL~~

Date: 17 December 2020  
Version: 4.0  
Status: Final  
Page: 50 of 110

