**Novo Nordisk**

**Table 5-5 Statistical analysis to address primary and secondary objectives**

SI No	Endpoints	Landmark visit	Endpoint type	Imputation approach and Statistical model	Analysis set	Sensitivity analyses
Primary Endpoint						
1	Last planned HbA 1c prior to delivery after GW 16	Last planned visit prior to delivery after GW 16	Continuous	MI ANCOVA	FAS pregnant	
 
MI based on the PPpregnant
 
MI tipping point analysis based on the FASpregnant
 

Secondary Endpoint						
1	HbA 1c ≤ 6.0% (42 mmol/mol) from last planned HbA 1c prior to delivery after GW 16 (yes/no)	Last planned visit prior to delivery after GW 16	Categorical	MI Logistic regression	FAS pregnant	NA
2	HbA 1c ≤ 6.5% (48 mmol/mol) from last planned HbA 1c prior to delivery after GW 16 (yes/no)	Last planned visit prior to delivery after GW 16	Categorical	MI Logistic regression	FAS pregnant	NA
3	Last planned average PPG prior to delivery after GW 16	Last planned visit prior to delivery after GW 16	Continuous	MI ANCOVA	FAS pregnant	NA
4	Last planned FPG prior to delivery after GW 16	Last planned visit prior to delivery after GW 16	Continuous	MI ANCOVA	FAS pregnant	NA

Statistical Analysis Plan  
Trial ID: NN1250-4300  
UTN: U1111-1191-3018  
EudraCT No: 2017-000048-17

~~CONFIDENTIAL~~

Date: 27 January 2021  
Version: 2.0  
Status: Final  
Page: 24 of 34

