**Novo Nordisk**

## 5.4 Secondary endpoints analysis

### 5.4.1 Efficacy endpoints

#### 5.4.1.1 Supportive secondary endpoints

The supportive secondary endpoints will be evaluated for:

- The primary estimand based on  $FAS_{\text{pregnant}}$  using the in-trial data
- The secondary estimand based on  $FAS_{\text{pregnant}}$  using the on-treatment data

No sensitivity analyses are planned for these.

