#### Supportive maternal continuous efficacy endpoints

- Last planned average PPG prior to delivery after GW 16
  - Average of three main meals
- Last planned FPG prior to delivery after GW 16

Average PPG is defined as the average of the available BG measurements 90 minutes after breakfast, lunch and main evening meal respectively. If all 3 measurements are missing the average PPG is missing. Subjects with missing average PPG at baseline are excluded from the PPG analysis and subjects with missing FPG at baseline are excluded from the FPG analysis. The above continuous endpoints will be analysed using similar modelling approaches as for the primary endpoint with the associated baseline response as a covariate.

Statistical Analysis Plan  
 Trial ID: NN1250-4300  
 UTN: U1111-1191-3018  
 EudraCT No: 2017-000048-17

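### FPG and PPG share the HbA1c landmark visit, which can fall on V63 or V71, where neither is scheduled

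*SAP*

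**What the plan says.** In SAP Table 5-5 the landmark column reads "Last planned visit prior to delivery after GW 16" for HbA1c, both HbA1c targets, PPG and FPG alike. SAP 6.3.1.1 derives that visit once, for all endpoints. Step 3 opens "For subjects with visit 59, 63, 67, 71, or 75 as the last site visit prior to delivery the following is done". If delivery is at most 35 days after the last attended visit, that visit is the landmark; otherwise it is the next planned site visit, four weeks on.

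Protocol flowchart 2.3 has HbA1c at every pregnancy site visit up to V79. From GW 16, the row "Fasting plasma glucose", the 9-point profile row and the reminder "Attend visit fasting" are marked only at V59, V67, V75 and V79, and are blank at V63 and V71. The text agrees. Protocol 8.5.2 says "Subject must attend specific visits in a fasting condition as outlined in the flowchart", and Table 8-1 is titled "Time points for the 9-point profile collected 2 days before selected visits". SAP 5.4.1.1 builds PPG from the 90-minute post-meal values, which are points of that profile.

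For the analysis of FPG and PPG, SAP 5.4.1.1 prescribes "similar modelling approaches as for the primary endpoint with the associated baseline response as a covariate". It adds rules for a missing baseline and a partly missing PPG, but no rule on the visit. Of the supportive efficacy endpoints the SAP says "No sensitivity analyses are planned for these".

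**The concern.** A landmark rule that suits HbA1c, measured at every visit, has been carried over to two measurements taken at only some visits. When the rule lands on V63 or V71, there is no FPG or PPG to find.

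The protocol's fallback (17.3.1) looks only forward, to an additional visit before delivery. It does not look back to the previous scheduled measurement. The model holds the baseline response and no later value. A woman with a measured FPG at V59 or V67 would therefore enter the modelled comparison through a random draw, and her own last planned value would play no part. The draw would also come from a model fitted only to women with other landmarks, because no woman with a V63 or V71 landmark has a scheduled value to contribute.

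At stake is the faithful analysis of two supportive endpoints, and a programming choice (impute, look back or exclude) that a final SAP should not leave open.

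**Working it through.** **Inputs.** Visit weeks and the ±7-day window are from flowchart 2.3; the 35-day test is from SAP 6.3.1.1. I take each target as completed weeks plus 0 days: V59 = day 112, V63 = 140, V67 = 168, V71 = 196, V75 = 224, V79 = 252.

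**The SAP's own figure.** 28 days between site visits + 7 days of window = 35 days. This reproduces.

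**What is measured where.**

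| Visit | GW | HbA1c | FPG and profile | Can be the landmark |
|---|---|---|---|---|
| V59 | 16 | yes | yes | yes |
| V63 | 20 | yes | no | yes |
| V67 | 24 | yes | yes | yes |
| V71 | 28 | yes | no | yes |
| V75 | 32 | yes | yes | yes |
| V79 | 36 | yes | yes | yes |

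**Which deliveries are affected.** These are women whose landmark is V63 or V71 before the next FPG visit was due.

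- V63 attended on target: days 141 to 168, GW 20+1 to 24+0, 28 days.
- V71 attended on target: days 197 to 224, GW 28+1 to 32+0, 28 days.
- V63 missed, V59 on target: the gap exceeds 35 days from 112 + 36 = day 148, so GW 21+1 to 24+0, 21 days.
- V71 missed, V67 on target: from 168 + 36 = day 204, so GW 29+1 to 32+0, 21 days.
- Range over visit timing, V63 attended: the shortest span is V63 on day 147 and V67 on day 161, 161 − 147 = 14 days. The longest is V63 on day 133 and V67 on day 175, 42 days, which the 35-day test caps at 35.

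**Example.** FPG measured at V59 (GW 16+0), V63 attended (GW 20+0), delivery at GW 23+0 (day 161). The gap is 161 − 140 = 21 days, so the landmark is V63. FPG is missing by design and imputed, although the last planned FPG was obtained.

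**Scale, under assumptions.** The documents give no count of such women. SAP 6.3.1.1 has 188 women in the pregnant full analysis set, and the protocol assumes at most 10% deliver before GW 16: 188 × 0.9 = 169.2, or 84.6 per arm. Suppose 1 to 5 women in one arm have a value changed by 0.5 to 2 mmol/L (both assumed). The crude treatment difference then moves by 1 × 0.5 / 84.6 = 0.006 to 5 × 2 / 84.6 = 0.12 mmol/L.

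**The case against.** The best reply is that the endpoints are named last planned FPG and last planned average PPG. If the qualifier belongs to the measurement, an FPG is planned only at V59, V67, V75 and V79, so V63 and V71 can never be its visit and nothing measured is lost. That reading is possible, and it means the documents do not prove that values will be discarded. But the SAP nowhere states it. The landmark column of Table 5-5 and the single derived variable point the other way, and SAP 5.4.1.1 adds FPG- and PPG-specific rules without adding this one.

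Second, the consequence is low. The endpoints are supportive, and protocol 17.4.1 plans summaries and plots by arm and visit, so measured V59 and V67 values would still be shown. That stands; the loss is confined to the modelled contrast.

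Third, not every V63 or V71 landmark does harm. A woman last seen at V67 who delivers at GW 38+0 gets V71, but her V75 and V79 values were planned and not obtained, so imputation is right on either reading. That also stands, and such cases are left out of the ranges above.

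A reader might go further and infer that the primary endpoint is compromised, because Step 3 counts from the actual visit date while Step 4 sets V79 for any Covid-19 miss. The two can diverge. With V75 at GW 33+0 and delivery at 37+5, the gap is 264 − 231 = 33 days and V75 is kept, yet V79 is set if its miss was registered as Covid-19. But this needs a narrow set of dates. If 1 to 5 women in one arm carried a value differing by 0.1 to 0.3 points (assumed), the shift is 0.1 / 84.6 = 0.001 to 1.5 / 84.6 = 0.018 points, against a margin of 0.4. Using an HbA1c observed within 35 days of delivery is a defensible tolerance, and a stricter rule would trade observed values for imputed ones. I would not change the HbA1c steps.

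**Conclusion.** The point holds for FPG and PPG. As written, the SAP can assign them a landmark at which they are not scheduled, and then imputes a value although the last planned one may have been measured. With visits on target this covers deliveries in two 28-day spans, GW 20+1 to 24+0 and 28+1 to 32+0. The spans rest on the literal reading of Table 5-5 and on targets at completed weeks plus 0 days.

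The number of women is unknown and probably small. The protocol's 6% missing-data figure cannot stand in for it, because that figure concerns withdrawal and not early delivery. The 0.006 to 0.12 mmol/L range is an illustration under assumed inputs and not an estimate.

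The mechanism does not reach the primary endpoint: HbA1c is scheduled at every possible landmark visit, so the documents give no ground for inferring that the non-inferiority conclusion is at risk.

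**What to change.** In SAP 6.3.1.1 and Table 5-5, define a separate landmark for FPG and PPG: the last visit before delivery at which that assessment was scheduled, out of V59, V67, V75 and V79.

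The 35-day test does not fit here, because V59 to V67 and V67 to V75 are 56 days apart. Replace it, for these two endpoints only, by the close of the window of the next scheduled FPG/profile visit:

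- keep V59 for deliveries up to 168 + 7 = day 175, GW 25+0;
- keep V67 up to 224 + 7 = day 231, GW 33+0;
- keep V75 up to 252 + 7 = day 259, GW 37+0.

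For later deliveries, set the landmark to that next visit and treat its value as missing. Apply Steps 4 and 5 unchanged, and leave the HbA1c derivation as it is.

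The cost is some SAP text and one more derived variable; visit dates, gestational age and delivery date are already collected. The SAP should state the trade-off. A retained V59 or V67 value may lie 175 − 112 = 231 − 168 = 63 days (9 weeks) before delivery if the visit was on target, and 70 days (10 weeks) if it was 7 days early.
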